8.2. Discussion of Design and Control

A randomized, controlled design is being used in this study. Randomization minimizes systematic bias in the selection and assignment of patients to study treatment and provides justification for inferential statistical methods to be used on data from this study. Using an appropriate concurrent control arm enables direct statistical estimation of benefits and harms due to study treatment and minimizes bias in the assessment and interpretation of observed treatment effects.

To further reduce the potential for bias and improve the power of the analyses, patients will be stratified for differences in factors thought to be associated with clinical outcomes. Assessment of bias is further minimized by the use of a double blind and placebo control.

Currently, no agent has improved survival of patients with advanced HCC over BSC following progression on and/or intolerance to sorafenib. Given the lack of a regimen specifically approved in this setting, or an established standard of care, single-agent ramucirumab (plus BSC) was selected for the investigational arm to allow demonstration of potential benefit with ramucirumab. Placebo plus BSC is considered an appropriate control in this setting consistent with current guidelines on HCC (Llovet et al. 2008a; Thomas et al. 2010; EASL-EORTC 2012).

9. Treatment

9.1. Treatments Administered

The following treatments will be administered in this study:

- Arm A: ramucirumab 8 mg/kg
- Arm B: placebo (equivalent volume)

Study treatment (ramucirumab or placebo) will be administered as an intravenous infusion once per 14-day cycle. See Section 9.4 for more information about the timing of study treatment. All patients will receive BSC.

The investigator or his/her designee is responsible for the following:

- explaining the correct use of the drug and planned duration of each individual's treatment to the patient, site personnel, and, if applicable, the patient's legal representative,
- verifying that instructions are followed properly,
- maintaining accurate records of drug dispensing and collection,
- and returning all unused medication to Lilly or its designee at the end of the study.

Note: In some cases, sites may destroy clinical trial material if, during the investigative site selection, the evaluator has verified and documented that the site has appropriate facilities and written procedures to dispose of clinical trial materials.

Patients will be instructed to contact the investigator as soon as possible if they have a complaint or problem with the study drug so that the situation can be assessed.

9.2. Materials and Supplies

Ramucirumab and placebo will be provided by Lilly and will be labeled according to the country's regulatory requirements.

9.2.1. Ramucirumab

All excipients used for the manufacture of ramucirumab are of pharmacopeial grade. No animal-derived components are used in the manufacture of ramucirumab excipients.

Refer to the most current version of the ramucirumab IB for safe handling and administration details.

9.2.2. Placebo

All excipients used for the manufacture of placebo are of pharmacopeial grade. No animal-derived components are used in the manufacture of placebo excipients.

9.3. Method of Assignment to Treatment

After the patient signs the ICF, the site will register the patient via the Interactive Web Response System (IWRS), which is accessible 24 hours a day. IWRS registration consists of assigning the patient a unique study identification number, after which screening for eligibility may commence. Upon completion of all screening evaluations to confirm a patient's eligibility, sites will utilize IWRS to randomize the patient to 1 of the 2 treatment arms. Once the patient is randomized through the IWRS, he/she is considered to be enrolled in the study.

Randomization will be stratified by the following factors:

1. geographic region (Region 1 versus Region 2 versus Region 3)
2. macrovascular invasion (yes versus no)
3. ECOG performance status (0 versus 1)

The general plan for assigning participating countries to a geographic region is as follows:

1. Region 1 will include the Americas, Europe, Israel, and Australia.
2. Region 2 will include countries in Asia (excluding Japan).
3. Region 3 will include Japan only.

Participating countries not specifically described above will be assigned to Region 1, 2, or 3, as deemed appropriate by the study team. Specific details about the countries assigned to each region will be provided in the statistical analysis plan (SAP).

9.4. Selection and Timing of Doses

A cycle is defined as an interval of 14 days. In Cycle 1, study treatment should be administered within 7 days after the patient's randomization date. If the Cycle 1 infusion cannot be administered within 7 days after the patient's randomization date, study treatment must be delayed until laboratory tests are repeated and the case is discussed with the Lilly CRP. See *Laboratory Evaluations* in the study schedule ([Attachment 1](#)).

In subsequent cycles, study treatment may be administered up to 3 days before or up to 3 days after the patient's scheduled dose.

The actual doses of ramucirumab and placebo to be administered will be determined by measuring the patient's weight in kilograms at the beginning of each cycle. If the patient's weight does not fluctuate by more than $\pm 10\%$ from the weight used to calculate the prior dose, the dose will not need to be recalculated. A $\pm 5\%$ variance in the calculated total dose will be allowed for ease of dose administration.

A patient may continue to receive study treatment until a criterion for discontinuation is met (as described in [Section 7.3](#)).

9.4.1. Preparation and Administration of Study Treatment

9.4.1.1. Preparation

Aseptic technique is to be used when preparing and handling study treatment for infusion.

Ramucirumab and placebo are compatible with common infusion containers. The use of a low protein binding 0.22-micron in-line filter is required. Details regarding infusion sets that are compatible for ramucirumab infusion can be found in the study pharmacy manual and the IB.

Based on the calculated volume of ramucirumab/placebo, add (or remove from pre-filled with 0.9% normal saline intravenous infusion container) a sufficient quantity of sterile normal saline (0.9% weight/volume) to the container to make the total volume 250 mL. For dose volumes greater than 250 mL, the addition of sterile normal saline is not required. Do not use dextrose-containing solutions. The container should be gently inverted to ensure adequate mixing. Further details regarding study drug preparation can be found in the study pharmacy manual and the IB.

9.4.1.2. Premedication

Premedication with a histamine H₁ antagonist, such as diphenhydramine hydrochloride (or equivalent), is required prior to infusion of ramucirumab/placebo. Additional premedication may be provided at the discretion of the investigator. See [Table JVDE.3](#) for dose modifications and additional premedication requirements for patients who have experienced a prior infusion-related reaction (IRR). All premedication administered must be adequately documented on the CRF.

9.4.1.3. Administration of Study Treatment

Treatment should commence only if all the inclusion and exclusion criteria are met, and the patient has been randomized to Arm A (ramucirumab) or Arm B (placebo) via IWRS. For subsequent cycles, dose modifications are permitted as described in Section 9.4.2. All study treatment will be discontinued in the event of disease progression (Section 7.3.2).

Prior to each infusion of study treatment, the patient must meet the criteria shown in [Table JVDE.1](#).

Table JVDE.1. Criteria to Be Met Prior to Each Infusion of Study Treatment

Event	Requirement
AESI	Refer to Table JVDE.3
Other clinically significant toxicity or AE related to study treatment, as determined by the investigator	The event must be resolved to CTCAE (Version 4.0) Grade <2 or the patient's baseline level

Abbreviations: AE = adverse event; AESI = adverse event of special interest; CTCAE = Common Toxicity Criteria for Adverse Events (NCI 2009).

Ramucirumab or placebo should be delivered via infusion pump in approximately 60 minutes. The infusion rate should not exceed 25 mg per minute. Infusions >60 minutes are permitted in

specific circumstances (that is, for larger patients in order to maintain an infusion rate that does not exceed 25 mg/minute, or in the setting of prior IRR); the infusion duration must always be accurately recorded. After the infusion, the infusion set must be flushed with sterile 0.9% normal saline greater than or equal to infusion set hold-up volume to ensure delivery of the calculated dose.

CAUTION: Infusion-related reactions (IRRs) may occur during or following administration of study treatment. During the infusion, patients should be in an area that has available resuscitation equipment and treatments necessary for advanced life support and cardiopulmonary resuscitation (CPR), such as bronchodilators, vasopressor agents (for example, epinephrine), oxygen, glucocorticoids, antihistamines, intravenous fluids, and so forth. A 1-hour observation period is required after the administration of the first 2 doses of ramucirumab. If no evidence of an IRR is observed during the initial 2 cycles of study treatment, then no observation period is required for subsequent treatment cycles. In the event an IRR occurs thereafter, then the 1-hour observation should be reinstated.

9.4.2. Dose Modifications

Dose modifications are permitted for non-life-threatening Grade 3 clinical AEs (such as fever) that are considered to be at least possibly related to study treatment and that resolve to Grade ≤ 1 or to the patient's pretreatment baseline level within 1 treatment cycle (approximately 2 weeks). Discontinue study treatment if the patient experiences a Grade 4 AE, other than Grade 4 fever or Grade 4 laboratory abnormalities, that is at least possibly related to study treatment.

Table JVDE.3 presents the criteria for dose modifications that are applicable if a patient experiences an adverse event that is considered an *adverse event of special interest* (AESI). A list of the AESIs is provided below. Detailed information about AESIs is provided in Section 10.3.1.1.

Infusion-related reactions (IRRs)	Gastrointestinal perforation
Hypertension	Congestive heart failure
Proteinuria	Wound healing complications
Arterial thromboembolic events (ATEs)	Fistula
Venous thromboembolic events (VTEs)	Liver failure/liver injury
Bleeding/hemorrhagic events	Reversible posterior leukoencephalopathy syndrome (RPLS)

Table JVDE.4 presents the criteria for dose modifications that apply if a patient experiences an AE that is not an AESI.

Any patient who requires a dose reduction will continue to receive a reduced dose until discontinuation from study treatment, or discontinuation from the study. No dose escalations are allowed after a dose reduction. Any patient who has had 2 dose reductions and who experiences a toxicity that would cause a third dose reduction, must be discontinued from study treatment.

Table JVDE.2 presents the specific dose reductions applicable to both treatment arms.

Table JVDE.2. Dose Reductions^a

	Dose
Starting dose	8 mg/kg
First dose reduction	6 mg/kg
Second dose reduction	5 mg/kg

^a Dose reductions are allowed between cycles and within a given cycle.

If a patient is unable to receive study treatment on the date of his/her regularly scheduled dose (± 3 days) for any reason (including AEs), the next dose of study treatment should be administered at the next regularly scheduled treatment time point following the resolution of the event that caused the delay (treatment in this situation is considered to occur at the numbered cycle immediately following the last cycle in which the patient received study treatment).

Make-up doses occurring between regularly scheduled (every-14-days) treatment time points are not permitted.

Study treatment may be delayed for up to 21 days to allow time for a patient to recover from an AE or laboratory toxicity. If a patient misses ≥ 2 consecutive doses or requires a dose delay of > 21 days, continuation of study treatment may be considered after consultation with the Lilly CRP, if both of the following criteria are met:

- the events related to the missed/delayed doses have been resolved
- the patient shows evidence of ongoing disease control

Table JVDE.3. Dose-Modification Guidelines for Adverse Events of Special Interest

Adverse Event of Special Interest		Dose Modification
1.	Infusion-related reaction (Section 10.3.1.1.1)	
1.a.	
 Infusion-related reaction - Grade 1 or 2 	
Reduce the infusion rate by 50% for the duration of the infusion and for all future infusions.
 
Prior to all future infusions, premedicate with:
 
 a histamine H1 antagonist, such as diphenhydramine hydrochloride dexamethasone or equivalent acetaminophen
1.b.	
 Infusion-related reaction - Grade 3 or 4 	Discontinue study treatment.
2.	Hypertension (Section 10.3.1.1.2)	
2.a.	
 Hypertension (non-life-threatening) - Grade 2 or 3 	
Delay ramucirumab until the hypertension is controlled with medication and is resolved to Grade <2.
 
 If controlled with medication and resolved to Grade <2, then resume study treatment at current dose. If not controlled with medication and not resolved to Grade <2 within 21 days, then discontinue study treatment. For patients with asymptomatic Grade 2 hypertension, investigators have the discretion to consider the clinical circumstances of individual patients and administer unchanged dose of study treatment.
2.b.	
 Uncontrolled hypertension, hypertensive crisis, or hypertensive encephalopathy - Grade 4 	Discontinue study treatment.
3.	Proteinuria (Section 10.3.1.1.3)	
3.a.	
 Proteinuria =2+ (dipstick or routine urinalysis)^a 	
 Administer study treatment at the patient's current dose if clinically indicated. Obtain 24-hour urine protein results within 3 days prior to the next infusion. 
 If urine protein is <2 g/24 h, administer study treatment at the patient's current dose. If urine protein is ≥2 g/24 h, modify the dose based on 24-hour collection. See Proteinuria ≥2 g/24 h (24-hour urine collection), Line 3.c in this table.
3.b.	
 Proteinuria >2+ (dipstick or routine urinalysis)^a 	
 Delay study treatment for up to 21 days. Obtain 24-hour urine protein results within 3 days prior to the next infusion. 
 If urine protein is <2 g/24 h, no further dose delay or dose reduction is required. If urine protein is ≥2 g/24 h, modify the dose based on 24-hour collection. See Proteinuria ≥2 g/24 h (24-hour urine collection), Line 3.c in this table.

Adverse Event of Special Interest		Dose Modification
3.c.	
 Proteinuria ≥ 2 g/24 h (24-hour urine collection)^a 	
First or second occurrence: delay study treatment until urine protein returns to < 2 g/24 h. Reduce the dose as shown in Table JVDE.2.
 
If urine protein remains ≥ 2 g/24 h after 21 days, discontinue study treatment.
 
Third occurrence: discontinue study treatment.

3.d.	
 Proteinuria > 3 g/24 h or in the setting of nephrotic syndrome^a 	Discontinue study treatment.
4.	Arterial thromboembolic events, venous thromboembolic events (Section 10.3.1.1.4) - Grade 3 or 4	Discontinue study treatment.
5.	Bleeding (Section 10.3.1.1.5) - Grade 3 or 4	Discontinue study treatment.
6.	Gastrointestinal perforation (Section 10.3.1.1.6)	Discontinue study treatment.
7.	Reversible posterior leukoencephalopathy syndrome (Section 10.3.1.1.7)	Discontinue study treatment.
8.	Congestive heart failure (Section 10.3.1.1.8) – Grade 3 or 4	Discontinue study treatment.
9.	Fistula formation (Section 10.3.1.1.9)	Discontinue study treatment.
10.	Impaired wound healing (Section 10.3.1.1.10)	
10.a.	
 Prior to planned surgery 	Withhold study treatment.
10.b.	
 After surgery 	Resume study treatment based on clinical judgment (maximum delay is 21 days).
10.c.	
 Wound-healing complications developed during study treatment 	Delay study treatment dosing (for up to 21 days) until the wound is fully healed.
11.	Liver injury/liver failure (Section 10.3.1.1.11)	
11.a.	
 Hepatic encephalopathy and/or hepatorenal syndrome 	Discontinue study treatment.

^a Perform dipstick or routine urinalysis within 72 hours prior to each infusion of ramucirumab (see [Table JVDE.1](#)). If 24-hour urine collection is also performed, the results of 24-hour urine collection should be used for clinical decision-making.

Table JVDE.4. Dose Modifications for Adverse Events That Are Not Adverse Events of Special Interest

AE or Toxicity	Dose Modification	

Grade 2 clinical AE or Grade 2 laboratory abnormality that is (a) reversible and (b) not life-threatening
 
Grade 3 laboratory abnormality that is: (a) not clinically significant and (b) unrelated to study treatment
	At the discretion of the investigator, study treatment may be delayed for up to 21 days.	
	Dose reduction is not required.	

Grade 3 or 4 clinical AE that is unrelated to study treatment
 
Grade 4 laboratory abnormality that is: (a) clinically insignificant and (b) unrelated to study treatment
	At the discretion of the investigator, study treatment may be delayed for up to 21 days. If the investigator chooses to delay study treatment, follow the instructions below:	
	If the event resolves to Grade <2 or the patient's baseline level within 21 days	Then , resume study treatment, at the discretion of the investigator. Dose reduction is not required.
	If the event does not resolve to Grade <2 or the patient's baseline level within 21 days	Then , discontinue study treatment.

Grade 3 clinical AE that is at least possibly related to study treatment
	Delay study treatment for up to 21 days.	
	If the event resolves to Grade <2 or the patient's baseline level within 21 days	Then , resume study treatment at a reduced dose, as shown in Table JVDE.2 .
	If the event does not resolve Grade <2 or the patient's baseline level within 21 days	Then , discontinue study treatment.

Grade 3 or 4 fever that is at least possibly related to study treatment
 
Grade 3 laboratory abnormality that is: (a) clinically significant or (b) at least possibly related to study treatment
 
Grade 4 laboratory abnormality that is at least possibly related to study treatment
	Delay study treatment for up to 21 days	
	If the event resolves to Grade <2 or the patient's baseline level within 21 days:	
	
 First occurrence: 	Then , resume study treatment, at the discretion of the investigator. Dose reduction is not required.
	
 Second occurrence of the same event: 	Then , resume study treatment at a reduced dose, as shown in Table JVDE.2 .
	If the event does not resolve Grade <2 or the patient's baseline level within 21 days	Then , discontinue study treatment.
Any other Grade 4 clinical AE that is at least possibly related to study treatment	Discontinue study treatment.	

Abbreviation: AE = adverse event.

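### A 24-hour urine protein above 3 g meets two rows of Protocol Table JVDE.3 that disagree when a first or second occurrence resolves within 21 days

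*Protocol*

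**What the plan says.** All the operative text is in Protocol Section 9.4.2, Table JVDE.3, item 3 (proteinuria).

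- **Lines 3.a and 3.b** start from a dipstick or routine urinalysis result (equal to 2+, or above 2+) and order a 24-hour collection. Both then say "If urine protein is ≥2 g/24 h, modify the dose based on 24-hour collection" and refer the reader to "Line 3.c in this table". Neither mentions line 3.d.
- **Line 3.c** applies at 2 g/24 h or more and has no upper limit. Its instructions are "First or second occurrence: delay study treatment until urine protein returns to < 2 g/24 h" and "Reduce the dose as shown in Table JVDE.2". It has two exits to discontinuation: "If urine protein remains ≥ 2 g/24 h after 21 days, discontinue study treatment" and "Third occurrence: discontinue study treatment".
- **Line 3.d** applies to "Proteinuria > 3 g/24 h or in the setting of nephrotic syndrome". Its action is discontinuation, with no occurrence count and no waiting period.

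Footnote a to the table says that a 24-hour result, where available, is the one to act on. Section 7.3.2 lists unacceptable toxicity as a reason for discontinuation and refers to this table for details. Section 10.3.1.1.3 sets a urine protein condition to be met before each dose and also refers back to the table.

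**The concern.** Every value above 3 g is also at least 2 g, so the two rows are not mutually exclusive. Two sites with the same laboratory result could each follow the written protocol, one restarting treatment at a reduced dose and the other stopping it for good. Proteinuria is a named adverse event of special interest, so the rule in question is a safety rule. An error in either direction has a cost to the patient: re-exposure in one case, loss of study treatment in the other.

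There is a smaller reporting consequence. The SAP summarises dose adjustments and their reasons (6.5.6.1), and adverse events leading to discontinuation and to dose modification (6.5.6.2 and 6.5.6.4). For the affected patients, the category in which they are counted would depend on how the site read the table.

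**Working it through.** No sample-size or power figure enters this point. The check is to apply the conditions of lines 3.c and 3.d to a range of 24-hour results by occurrence, and then to look for a precedence rule.

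**Inputs** (Table JVDE.3): line 3.c applies if protein ≥ 2 g/24 h; line 3.d applies if protein > 3 g/24 h. Nephrotic syndrome, the other trigger of line 3.d, is taken as absent.

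| 24-hour protein (g) | Occurrence | Line 3.c | Line 3.d | Agree? |
|---|---|---|---|---|
| 1.9 | any | does not apply | does not apply | – |
| 2.0, 2.5, 3.0 | 1st or 2nd | delay, then reduce | does not apply | no conflict |
| 2.0, 2.5, 3.0 | 3rd | discontinue | does not apply | no conflict |
| 3.01, 3.5, 5.0 | 1st or 2nd | delay, then reduce | discontinue | **no** |
| 3.01, 3.5, 5.0 | 3rd | discontinue | discontinue | yes |

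The disagreement is confined to the fourth row, and the 21-day condition in line 3.c narrows it further:

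- Still 2 g or more after 21 days: line 3.c also discontinues, so the rows end in the same place.
- Below 2 g within 21 days: line 3.c leads to resumption at a reduced dose, line 3.d to discontinuation. This is the contradiction.

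It also requires that a reduction step is left. Section 9.4.2 requires discontinuation when a patient who has already had two reductions would need a third, and the rows then coincide again.

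While protein is at 2 g or more, neither row leads to dosing at that level: line 3.c holds the dose and line 3.d ends treatment. The pre-dose condition in Section 10.3.1.1.3, which is below 2 g on a 24-hour collection, is consistent with that.

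**Is the missing upper limit a transcription fault?** No. Lines 3.a and 3.b repeat the title of line 3.c, again without an upper limit.

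**Does any text rank line 3.d over line 3.c?**

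- Footnote a ranks the 24-hour result over the dipstick. Both rows use the 24-hour result, so it does not choose between them.
- Section 7.3.2 refers to the table without ordering its rows.
- Section 10.3.1.1.3 refers to the table for dose modification.
- Table JVDE.1, the pre-infusion criteria, also refers to Table JVDE.3 for these events.
- Section 10.3.1.1 invites questions to the sponsor's clinical research physician and states no rule.

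None of these supplies a precedence rule. Nor does the table's layout suggest one: its other paired rows are disjoint (1.a Grade 1 or 2 against 1.b Grade 3 or 4; 2.a Grade 2 or 3 against 2.b Grade 4; 3.a equal to 2+ against 3.b above 2+).

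**The case against.** The best reply is that the table resolves itself. If line 3.c governed every result of 2 g or more, the quantity trigger in line 3.d would have almost no function. The rows are adjacent and escalate, so the ordinary reading is that 3.d carves the values above 3 g out of 3.c. On this view line 3.d needs no pointer, because its own trigger is a 24-hour quantity, and Section 7.3.2 brings the table's discontinuation rows into force in any case. A site in doubt can ask the sponsor's physician.

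Much of this is fair. The carve-out may well be what was meant. But it is an inference: no sentence states it, and the only explicit routing, in lines 3.a and 3.b, names line 3.c. The query route helps a site that notices the overlap. It does not help one that follows the pointer and sees no question to ask.

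The reply does defeat several stronger readings:

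- *That the rows give opposite actions for every result above 3 g.* They do not: line 3.c also discontinues at a third occurrence and when protein has not fallen below 2 g after 21 days.
- *That lines 3.a and 3.b switch line 3.d off.* They omit it. They do not say that line 3.c is the only row that can apply.
- *That few patients would be affected.* Section 10.3.1.1.3 says that most proteinuria events were Grade 1 or 2 and that the previous HCC trial had none of Grade 4 or 5. The documents do not map those grades to grams per 24 hours and give no count above 3 g, so that inference has no basis either.
- *That sites did act differently.* Nothing in the documents shows this.

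**Conclusion.** Table JVDE.3 contradicts itself for a 24-hour urine protein above 3 g at a first or second occurrence that falls below 2 g within 21 days. Line 3.c then leads to resumption at a reduced dose, line 3.d to discontinuation, and nothing in the protocol says which prevails. This is wrong as written, since two instructions conflict, rather than a detail left open. Severity is low.

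The number of patients affected cannot be derived from the documents. The conclusion rests only on the literal thresholds and on the absence of a precedence rule in the sections checked.

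A reader might infer a threat to the efficacy conclusions. The documents do not support that. The primary analysis is overall survival in all randomized patients as randomized (Protocol 12.2.6, SAP 6.5.3.2), tumour assessments continue after discontinuation for reasons other than radiographic progression where feasible (Protocol 7.3.2), and the per-protocol exclusions in SAP 6.3.3 do not include dose-modification handling. The effect is on patient safety and on descriptive summaries of dose modification and discontinuation.

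**What to change.** Reconcile lines 3.a to 3.d of Table JVDE.3. Word lines 3.c and 3.d so that no result can fall in both, including through the nephrotic-syndrome trigger of line 3.d. Change the cross-reference in lines 3.a and 3.b so that it names every row that can apply to the 24-hour result. Which action applies above 3 g/24 h is for the sponsor's clinical team to decide; this review takes no position on it.

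The cost is a few words in one table of the protocol. No change to the sample size or to any SAP analysis follows.
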